7.6. Subsequent Sessions

Those randomised to the experimental group will be asked to attend for 1 hour per week over the next 3 months at the Skills lab in the Nuffield Orthopaedic Centre for regular simulation training. Motion data may also be recorded during these sessions.

At 3 month follow up, all participants will repeat a simulated arthroscopy assessment lasting about 30-45 mins, similar to that which occurred at baseline, and an in theatre assessment using the same wireless elbow sensors. We aim to coordinate these two events in the same visit.

Junior surgical trainees perform surgery under consultant supervision as part of their training programme. It is during one of these surgical cases, we will gather objective surgical motion data in addition to the usual forms of educational evaluation which take place as part of training.

Participants will attend a consultant supervised knee arthroscopy list at the Nuffield Orthopaedic Centre. The participant and consultant will have the wireless sensors attached to their elbows by adhesive tape or custom sleeves that fit to the elbow. They are securely attached to the surgeon's elbows and do not interfere with thorough surgical scrubbing, nor do they interfere with any theatre equipment. The participant will scrub for the case with the consultant. The consultant will perform the procedure the patient has been admitted for, and once complete, will demonstrate a diagnostic knee arthroscopy (a

keyhole video examination of all the structures within the knee) to the participant as per standard surgical training practise. The consultant will then supervise the participant performing the same procedure as would normally happen during surgical training. They will provide the same support, and interrupt the procedure as they would in any other supervised surgical case if they feel this is necessary.

Participants motion analysis parameters will be compared to those of the supervising consultant, which will act as a bench-marking process to account for the technical differences between cases (e.g. the weight or size of the leg). This wireless motion data will be recorded to assess the elbow sensors' effectiveness at monitoring learning and performance in addition to the usual forms of educational monitoring e.g. Procedure-base assessments and global rating scales.

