8. STATISTICS AND ANALYSIS

8.1. Description of Statistical Methods

Motion analysis data from the elbow-worn wireless motion sensors produces similar data to the wired sensors our group has used previously.

Number of movements and path length are common to both devices. Data distributions will be assessed for normality. Previous studies show such data are not normally distributed and we would expect to use non-parametric tests, in this case the Mann-Whitney U test or Kruskal-Wallis test, to compare performance between groups during a given task. Mann-Whitney U tests will also be used within a group to compare performance before and after training on a simulator.

Surgical logbook data will be assessed using descriptive statistics, and motion analysis performance will be reported with reference to surgical experience.

Questionnaire data regarding the trainee and consultant perception of the utility of these sensors will be reported as descriptive statistics.

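### Section 8.1 names only unpaired tests, which, if used for the trainee–consultant comparison in 7.6, ignore both pairing within a case and repeated recording of consultants

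*Combined protocol and SAP*

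**What the plan says.** Section 7.6 sets out the 3-month theatre assessment. It takes place at one centre: "Participants will attend a consultant supervised knee arthroscopy list at the Nuffield Orthopaedic Centre". In each assessed case, "The participant and consultant will have the wireless sensors attached to their elbows". The consultant completes the patient's operation and then demonstrates a diagnostic arthroscopy; after that, "The consultant will then supervise the participant performing the same procedure as would normally happen during surgical training". So there are two recordings per case, from one knee.

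The comparison is planned in the same section: "Participants motion analysis parameters will be compared to those of the supervising consultant, which will act as a bench-marking process". The stated reason is to allow for technical differences between cases, such as leg size. The consultant can also affect the trainee's recording directly: "They will provide the same support, and interrupt the procedure as they would in any other supervised surgical case".

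Section 8.1 is the only methods section. For between-group comparisons it names "the Mann-Whitney U test or Kruskal-Wallis test, to compare performance between groups during a given task". It gives no paired test, consultant term, case term or allowance for clustering. Section 5 gives up to 60 trainees, randomised 50:50. Section 7.4 uses sealed envelopes and mentions no stratification by consultant. No section states the number of consultants or a cap on recordings per consultant.

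**The concern.** Mann-Whitney and Kruskal-Wallis tests need independent observations. The theatre data depart from that in two ways.

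- **Clustering.** With up to 60 trainees at one centre, some consultants will probably be recorded several times. A test that counts each recording as a separate expert overstates the information about consultants.
- **Pairing.** Trainee and consultant work on the same knee, so their recordings share a case effect. An unpaired test leaves that shared variation in the error term and understates the precision of the difference.

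The two faults act in opposite directions, so the direction of the net error depends on quantities that the plan does not give. The primary objective is the usefulness of the sensors in theatre, and section 3 suggests that surgical competence could be defined by these parameters. A trainee–consultant difference with the wrong precision would be a weak basis for that.

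**Working it through.** **Reference figure.** The planned 60 cannot be reproduced: section 8.2 gives no alpha, power, effect or SD.

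**From the documents:** up to 60 trainees, 1:1 allocation, one theatre assessment each, two recordings per case.

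**Assumed:** 60 cases spread evenly over J consultants, so m = 60/J recordings per consultant; ICC_c, the correlation among one consultant's own recordings; ICC_s, the correlation among different trainees under one supervisor; k, the share of variance due to the case; the two consultant-level effects independent; two-sided alpha 0.05.

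**Trainee against consultant, unpaired test.** The true variance of the mean difference divided by the variance that an unpaired analysis assumes is

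V = [2 + (ICC_c + ICC_s)(m − 1) − 2k] / 2

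and the approximate type I error is 2[1 − Φ(1.96/√V)].

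Example with J = 6, m = 10, ICC_c = 0.3, ICC_s = 0, k = 0.2: V = (2 + 0.3 × 9 − 0.4)/2 = 2.15. Then 1.96/√2.15 = 1.34, and the error is about 18%. The standard error is understated by a factor of √2.15 = 1.47.

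The last column is a simulation of the Mann-Whitney test under the null (3,000 runs per row, ICC_s = 0).

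| Consultants | ICC_c | k | V | Formula | Simulated |
|---|---|---|---|---|---|
| 6 | 0.3 | 0 | 2.35 | 20% | 19% |
| 6 | 0.3 | 0.2 | 2.15 | 18% | 20% |
| 6 | 0.3 | 0.4 | 1.95 | 16% | 17% |
| 10 | 0.3 | 0 | 1.75 | 14% | 14% |
| 10 | 0.3 | 0.2 | 1.55 | 12% | 12% |
| 10 | 0.3 | 0.4 | 1.35 | 9% | 9% |
| 10 | 0.1 | 0 | 1.25 | 8% | 9% |
| 10 | 0.1 | 0.1 | 1.15 | 7% | 6% |
| 10 | 0.1 | 0.2 | 1.05 | 6% | 6% |
| 10 | 0.1 | 0.4 | 0.85 | 3% | 3% |

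Simulated values vary by a point or two between runs (14–17% for 6 consultants, ICC 0.3, k = 0.4).

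The direction changes where (ICC_c + ICC_s)(m − 1) = 2k. With 10 consultants and ICC_c = 0.1, that is k = 0.1 × 5/2 = 0.25. With 6 consultants and ICC_c = 0.3, it would need k = 0.3 × 9/2 = 1.35, which is impossible for a share, so there the test is always too liberal. If 60 consultants are each recorded once with k = 0.2, V = 0.8 and the error is about 3%.

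**Pairing alone does not solve it.** For a signed-rank test over all cases the ratio is about [2 − 2k + (ICC_c + ICC_s)(m − 1)]/(2 − 2k). With 6 consultants, ICC_c = 0.3 and k = 0.2 this is (1.6 + 2.7)/1.6 = 2.69, an error of about 23% (simulated 23–25%). A t-test on one mean within-case difference per consultant, with J − 1 degrees of freedom, stayed at 5–6% in every setting tried.

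**Randomised arms, 30 per arm.** With consultant assignment unrelated to arm, the simulated type I error of the Mann-Whitney test was 4–6% throughout. For an assumed 0.74 SD effect, the unadjusted t-test has 80% power. With fixed consultant effects, the noncentrality is 0.74√[15(60 − J)/59/(1 − ICC_s)] on 59 − J degrees of freedom:

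| ICC_s | J = 4 | J = 6 | J = 10 |
|---|---|---|---|
| 0 | 78% | 77% | 73% |
| 0.1 | 82% | 81% | 78% |
| 0.2 | 87% | 85% | 82% |
| 0.4 | 94% | 94% | 92% |

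Adjustment gains 11–14 points at ICC_s = 0.4, about 2–6 at 0.2 and at most about 2 at 0.1. It loses 2–7 points if there is no consultant effect.

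**The case against.** The strongest reply is that section 8.1 names no trainee–consultant test. Its only explicitly defined groups are the two randomised arms, and 7.6 describes the consultant as a benchmark within each case. A reader might infer that the plan commits to pooling repeated consultant recordings as if they came from different experts; it does not say so. The link is a fair inference and no more: 7.6 plans the comparison, 8.1 is the only methods section, Kruskal-Wallis implies more than two groups, and section 5 lists consultants among the groups assessed. If 8.1 does not cover the comparison, then no method is given for it.

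A second reply is that the shared knee makes an unpaired test conservative. That stands in part. A reader might infer that the p-values will be too small; the documents do not support that, because the number of consultants, the ICCs and the case share are all unstated, and plausible values give errors below as well as above 5%.

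A third is that bench-marking already deals with consultant differences. Its stated purpose is to allow for differences between cases, and 8.1 never turns it into an analysis. Subtracting the consultant's value also brings that consultant's own level into every score.

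Finally, a reader might infer that the arm comparison is invalid or certain to lose power. Neither follows. Trainees are randomised individually, and adjustment can cost power when consultants differ little.

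**Conclusion.** The point holds in conditional form. The plan has no stated method that respects the structure of the trainee–consultant data, and the tests in 8.1 would ignore both case and consultant. The error would be serious if few consultants supply many cases and their recordings are moderately correlated. It would be small, or on the conservative side, if the consultant ICC is low and the shared-case effect is large. Every magnitude rests on assumed consultant numbers, ICCs and case shares.

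For the randomised arms there is no validity problem, provided that the list a trainee attends at 3 months does not depend on arm, which the documents do not state. Adjusting that comparison for consultant is an efficiency choice.

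**What to change.** 1. Record a coded consultant identifier against each theatre case, at the time of the case. Report the number of consultants and the cases per consultant.
2. In 8.1, name the trainee–consultant comparison and define the benchmarked outcome. Replace the unpaired test with a model on log-transformed or ranked metrics with random effects for consultant and case, using small-sample degrees of freedom. Alternatively, analyse one mean within-case difference per consultant.
3. State that repeated consultant recordings will not enter a Mann-Whitney, Kruskal-Wallis or all-case signed-rank test as independent values. With few consultants, a signed-rank test on the summaries is not an option either: with 5 its smallest two-sided p-value is 2/32 = 0.06. A t-test on the summaries avoids this.
4. Optionally, pre-specify an arm comparison with a consultant effect as a supporting analysis. Avoid a fully stratified rank test if there are many consultants: with 10 and no consultant effect, simulated power fell from 77% to 64%.

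The cost is one coded field and a little more analysis work. If consultant is added to the arm comparison and has no real effect, power falls by about 2–6 points with aligned ranks (6 and 10 consultants, 0.6 SD effect) or 2–7 with fixed effects.

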1. SYNOPSIS

Study Title	'Simulation-based Arthroscopic Surgery Programme' (MSD-IDREC-C1-2014-152)	
Internal ref. no. / short title		
Study Design	Educational observational study	
Study Participants	Healthy Volunteers from junior surgical trainees, and their consultants, working within the Oxford Deanery (Health Education Thames Valley)	
Planned Sample Size	60 per year	
Planned Study Period	5 years (to 2019)	
	Objectives	Outcome Measures
Primary	Assess the usefulness to training of the new elbow-attached motion sensors during diagnostic knee arthroscopy as part of routine consultant-supervised training in theatre	Motion data, Global Rating Scales, Surgical logbook data
Secondary	Assess the usefulness to training of the new elbow-attached motion sensors during simulated arthroscopy in the skills lab	Motion data, Surgical logbook data

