Generalisable findings: Initially we aim to assess the motion parameters associated with diagnostic knee arthroscopy (a single repeatable arthroscopic tasks), but the concept and techniques of in theatre motion analysis could be generalised to all procedures where technical skills are required. The use of motion analysis intra-operatively means that surgical competence could be defined in terms of motion analysis parameters. Correlation between simulated and intra-operative measurements of these motion analysis parameters could be used to define a proficiency criterion in simulated pre-patient training before performing surgery in theatre, or motion analysis parameter correlation with the number of procedures performed could be used to advise the SAC when defining the indicative numbers of procedures required to achieve CCT.

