4. OBJECTIVES AND OUTCOME MEASURES

Objectives	Outcome Measures	Timepoint(s) of evaluation of this outcome measure (if applicable)

Primary Objective Assess the usefulness of the new elbow-attached motion sensors during diagnostic knee arthroscopy as part of routine, consultant-
	
Motion analysis parameters during consultant-supervised diagnostic knee arthroscopy
 
Global rating scale during consultant-supervised diagnostic
	
At 3 months follow up, as part of and during the CUREC-approved 'Simulation-based Arthroscopic Surgery Programme' MSD-IDREC-2014-152

supervised training in theatre	knee arthroscopy	
Secondary Objective Assess the usefulness to training of the new elbow-attached motion sensors during simulated arthroscopy in the skills lab	Motion analysis parameters during simulated arthroscopy in the Skills lab	At baseline and after 3 months,

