5. STUDY DESIGN

The ‘Simulation-based Arthroscopic Surgery Programme’ MSD-IDREC-2014-152 is a CUREC-approved series of studies investigating the effect of new training methods for our future surgeons and using simulators, cadaver specimens and virtual reality models. These studies involve the assessment of trainee groups (including junior surgical trainees, specialist registrars and consultants) in two ways:

- 1 – on simulators, using metrics such as motion analysis data, global rating scales and participant feedback
- 2 – in theatre, using metrics such as global rating scales, procedure based assessments and participant feedback.

In this particular sub-study, we are recruiting up to 60 junior surgical trainees in T&O posts as part of their training programme. These will all undergo a baseline assessment on an arthroscopic simulator, after which they will be randomised 50:50 to either a control group (regular training i.e. their T&O post) or an experimental group (additional simulation training approx.. 1 hour per week) for the next three months. At 3 months they will undergo repeat assessment on the arthroscopic simulator, and in theatre.

Participants will use simple elbow-worn wireless motion sensors during simulation assessments and simulation training, and during usual training in theatre under consultant-supervision, while the patients received their normal treatment, to assess their effectiveness at monitoring learning and performance in addition to the usual forms of educational monitoring above. Over the course of the study, surgical logbook/training data will be collected by the participant and linked to their other results anonymously.

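### Section 8.1 names no inferential analysis clearly aimed at the primary objective: the in-theatre global rating scale is not analysed or related to the motion data

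*Combined protocol and SAP*

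**What the plan says.** The synopsis states the primary objective as "Assess the usefulness to training of the new elbow-attached motion sensors during diagnostic knee arthroscopy as part of routine consultant-supervised training in theatre". Section 5 says that participants wear the sensors "to assess their effectiveness at monitoring learning and performance in addition to the usual forms of educational monitoring above", and section 7.6 repeats that purpose for the theatre assessment. Section 4 lists two outcomes under the primary objective, both at 3 months: the in-theatre motion parameters and the "Global rating scale during consultant-supervised diagnostic" knee arthroscopy.

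Section 8.1 contains:

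- a "Mann-Whitney U test or Kruskal-Wallis test, to compare performance between groups during a given task", with no definition of the groups;
- a second use of the test: "Mann-Whitney U tests will also be used within a group to compare performance before and after training on a simulator";
- descriptive logbook statistics, with motion performance reported against surgical experience;
- a descriptive summary of a trainee and consultant questionnaire on the utility of the sensors.

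Section 7.6 adds that each trainee's motion parameters will be compared with the supervising consultant's, as a benchmark for differences between cases. Section 3 raises a further possibility: "Correlation between simulated and intra-operative measurements of these motion analysis parameters could be used to define a proficiency criterion".

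**The concern.** Whether a sensor usefully monitors performance is a question about measurement. It calls for evidence that the reading tracks performance as judged some other way. The plan collects such a reference, the GRS, beside the motion data and under the same objective, but section 8.1 does not use it.

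The randomised comparison does not fill the gap. Both arms wear sensors, so randomisation varies the training and not the use of the sensor. A null arm difference could mean that the extra simulation did not help or that the sensor does not register skill. A positive difference would show some responsiveness, but not how the sensor relates to the rating scale it is meant to supplement. The study could therefore finish with the relevant data in hand and no pre-specified inferential result on its primary objective.

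**Working it through.** **1. Planned analyses set against the primary objective (sensor usefulness, in theatre)**

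| Planned element | Where | Bearing on the primary objective |
|---|---|---|
| Mann-Whitney or Kruskal-Wallis between groups | 8.1 | Groups undefined. If they are the two arms, it tests training. If they are experience levels, it gives known-groups evidence on the sensor. |
| Before/after test | 8.1 | On the simulator, so it serves the secondary objective. Theatre is assessed only at 3 months (sections 4, 5, 7.6), so there is no before/after contrast there. |
| Motion reported by experience | 8.1 | Relevant, but no test or coefficient is named. |
| Utility questionnaire | 8.1 | Relevant, but descriptive, and absent from the outcome tables (sections 1, 4) and the visit descriptions (7.3, 7.6). |
| Trainee against consultant | 7.6 | Relevant, but no statistical method is given. |
| Simulator-theatre correlation | 3 | Mentioned as a possible use, not as a planned analysis. |
| GRS, alone or against motion data | none | No analysis. |

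**2. Why an arm difference is ambiguous**

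Let *d* be the effect of training on skill in SD units and *ρ* the correlation of the motion parameter with skill. If training changes the reading only through skill, the expected arm difference in the motion parameter is *d × ρ* SD. With assumed values, 0.5 × 0.7 = 0.35, and 0.7 × 0.5 = 0.35. A larger training effect seen through a weaker sensor gives the same result as a smaller effect seen through a better one. If either factor is zero, so is the product. The comparison cannot recover *ρ*, which is what the primary objective is about.

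**3. What a direct analysis could deliver**

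The plan has no figure to reproduce: section 8.2 gives no sample-size calculation. Inputs:

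- *n*: up to 60 trainees (section 5), a ceiling. *n* = 30 is shown as a lower case.
- *r*: assumed, since the documents give no correlation. It is shown as a magnitude. The sign should be negative if a higher GRS is better, because section 3 says movements and path length fall with experience.

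Approximate 95% CI for a Spearman correlation: tanh[atanh(r) ± 1.96 × √((1 + r²/2)/(n − 3))].

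For r = 0.5 and n = 60: atanh(0.5) = 0.549; SE = √(1.125/57) = 0.1405; 0.549 ± 0.275 = 0.274 to 0.825; back-transformed, 0.27 to 0.68.

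| n | assumed r | 95% CI |
|---|---|---|
| 60 | 0.3 | 0.04 to 0.52 |
| 60 | 0.5 | 0.27 to 0.68 |
| 60 | 0.7 | 0.52 to 0.82 |
| 30 | 0.3 | -0.08 to 0.60 |
| 30 | 0.5 | 0.15 to 0.74 |

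These intervals treat the pairs as independent. Trainees who share a supervising consultant would weaken that assumption.

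**The case against.** The best defence is that the objective is usefulness to training, not criterion validity against the GRS, and that the study is labelled educational and observational, where description is a legitimate choice. On that view the questionnaire, the reporting by experience, the performance curves in section 8.2 and the consultant benchmark already address usefulness. Kruskal-Wallis is normally used for three or more groups, and the programme includes junior trainees, registrars and consultants, so the group comparison may be across experience levels. Nor do the documents present the arm comparison as evidence on the sensor: section 7.8 gives a separate aim, the effectiveness of simulation training, which that comparison serves.

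Much of this stands, and it rules out two stronger readings. A reader might infer that comparing arms is the sole inferential analysis. The before/after test and the undefined groups contradict that. A reader might also infer that the plan has no means of addressing its primary question. It has several, though they are descriptive or lack a method.

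The defence does not explain why the GRS, an outcome listed under the primary objective, has no analysis. Nor does it settle what the groups are. If experience levels are meant, section 8.1 should say so.

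**Conclusion.** The point holds in this form: section 8.1 contains no inferential analysis clearly directed at the primary objective, and the in-theatre GRS is neither analysed nor related to the motion data. This rests on reading the sections together and on no numerical assumption. That an arm comparison alone is ambiguous follows from both arms wearing sensors.

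The intervals only illustrate that a direct analysis is feasible. At 60 trainees a moderate correlation would be estimated usefully, though not tightly; at 30 a weak one could not be distinguished from zero. It is tempting to go further and set the power of the arm comparison against that of a correlation. The documents give no effect size, SD or sensor-skill correlation, so such a contrast would mainly reflect the values chosen.

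This should be corrected. It is more than missing detail, because the change lets data already being collected address the primary objective.

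**What to change.** In section 8.1:

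1. **Primary objective.** Add the Spearman correlation, with 95% CI, between one motion parameter named in advance (number of movements or path length) and the in-theatre GRS at 3 months, all trainees pooled. Also report it with the parameter expressed relative to the supervising consultant's value in the same case. Use a CI that allows for trainees sharing a consultant, for example a bootstrap that resamples consultants or, if they are few, an analysis adjusted for consultant.
2. **Supporting analyses.** Add the simulator-theatre correlation of the same parameter at 3 months. Give a paired method, such as the Wilcoxon signed-rank test, for the trainee-consultant comparison already planned in section 7.6.
3. **Group comparisons.** Define the groups. Label the randomised comparison as the test of simulation training, and apply it to the GRS as well.

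The cost is protocol wording and a few extra analyses, with no added participants or visits. Section 9.1 already allows motion data to be matched to other metrics by unique identifier. The main drawback is that junior trainees span a narrow range of experience, which may lower the correlation; the report should say so when interpreting it.

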9. DATA MANAGEMENT

9.1. Access to Data

Direct access will be granted to authorised representatives from the Sponsor and host institution for monitoring and/or audit of the study to ensure compliance with regulations.

OSEC research team members will have access to raw motion data, and output metrics generated from the raw data. By unique identifiers, this can be matched to other metrics during the Simulation-based Arthroscopic Surgery Programme, but not de-anonymised to reveal participants or patients.

Our collaborator computer at MAT will have access to the raw motion data, and use this to produce algorithms to generate the performance output metrics. They will not require access to any files that matches participants to their unique identifiers, nor to non-motion sensor data generated by participants elsewhere in the study. As such, MAT computer scientists will not be able to link any motion data to participants.

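### The before/after simulator comparison applies the Mann-Whitney U test to the same trainees measured twice, which ignores the pairing, gives wrong p-values and can cost much of the power

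*Combined protocol and SAP*

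**What the plan says.** Section 8.1 expects motion data to be non-normal and plans rank tests. For comparisons between groups it names, "in this case the Mann-Whitney U test or Kruskal-Wallis test, to compare performance between groups during a given task". The next sentence extends the same test to change over time: "Mann-Whitney U tests will also be used within a group to compare performance before and after training on a simulator".

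The design sections describe who is measured and when:

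- Section 5, on the junior trainees recruited: "These will all undergo a baseline assessment on an arthroscopic simulator", and then "At 3 months they will undergo repeat assessment on the arthroscopic simulator, and in theatre".
- Section 7.6, on the 3-month visit: "all participants will repeat a simulated arthroscopy assessment lasting about 30-45 mins, similar to that which occurred at baseline".
- Section 4 lists simulator motion parameters as the outcome for the secondary objective, evaluated "At baseline and after 3 months".
- Section 9.1, on motion data: "By unique identifiers, this can be matched to other metrics during the Simulation-based Arthroscopic Surgery Programme". Section 7.4 gives each participant a unique identifier for motion capture.

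The document names no signed-rank test, paired test or repeated-measures model. It states no significance level, effect size, standard deviation, within-trainee correlation or power.

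**The concern.** The Mann-Whitney U test takes its null distribution from two independent samples. A trainee's baseline and 3-month scores on a similar task are two readings on one person, and skill scores on the same person normally correlate. The test leaves all the variation between trainees in the error term, although the design allows it to be removed.

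This is the only test the plan names for change within trainees, and Section 5 says the sensors are to be judged on how well they monitor learning. If a real improvement is declared non-significant because the pairing was discarded, the sensors could look less sensitive to learning than they are. Section 8.2 contains no sample-size calculation, so no planned power margin is available to absorb the loss.

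**Working it through.** The plan gives no figure for this comparison, so there is none to reproduce. The check measures what the stated test does to paired data.

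**Inputs from the documents**

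- Sub-study size: "we are recruiting up to 60 junior surgical trainees in T&O posts as part of their training programme" (Section 5), randomised 1:1. That gives at most 60 / 2 = 30 before/after pairs per group.
- Data shape: non-normal (Section 8.1).

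**Assumptions**

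- Two-sided 5% level.
- Within-trainee correlation ρ from 0 to 0.7.
- A true shift of 0.5 SD in the main table, with 0.3 and 0.8 SD as alternatives.
- Log-normal data with log-scale SD 0.5. Shifts are in SD units on the log scale.

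**Step 1: approximation on the scale of means**

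With n pairs, common variance σ² and correlation ρ, the true variance of the before/after difference is 2σ²(1 − ρ)/n. A test that assumes independence uses 2σ²/n, which is too large by a factor of 1/(1 − ρ). Hence, with Φ the standard normal distribution function:

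- True size of the unpaired test = 2[1 − Φ(1.96/√(1 − ρ))]. For ρ = 0.5 this is 2[1 − Φ(2.77)] = 0.6%. For ρ = 0.3 and 0.7 it is 1.9% and 0.03%.
- Unpaired power (n = 30, 0.5 SD, ρ = 0.5) = Φ[(0.5/√(2/30) − 1.96)/√0.5] = Φ[(1.936 − 1.960)/0.707] = 49%.
- Paired power, same case = Φ[0.5/√(2 × 0.5/30) − 1.96] = Φ(2.739 − 1.960) = Φ(0.779) = 78%.

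**Step 2: simulation of the rank tests themselves**

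Thirty pairs, 20,000 replicates per cell. Power is for a 0.5 SD shift.

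| ρ | Mann-Whitney true size | Mann-Whitney power | Signed-rank power, raw differences | Signed-rank power, log differences |
|---|---|---|---|---|
| 0 | 4.9% | 45% | 43% | 45% |
| 0.3 | 2.2% | 44% | 57% | 59% |
| 0.5 | 0.8% | 44% | 71% | 73% |
| 0.7 | 0.1% | 43% | 89% | 92% |

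The signed-rank test kept its size at about 5% throughout. With more skew (log-scale SD 1), signed-rank power on raw differences at ρ = 0.3, 0.5 and 0.7 falls to 53%, 66% and 86%. Mann-Whitney depends only on ranks and is unaffected by the scale.

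**Step 3: other cases (Mann-Whitney against signed-rank on raw differences, log-scale SD 0.5)**

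- 30 pairs, 0.3 SD, ρ = 0.5: 12% against 33%.
- 30 pairs, 0.8 SD, ρ = 0.5: 91% against 98%.
- 15 pairs, 0.5 SD, ρ = 0.5: 18% against 40%.
- 30 pairs, ρ = −0.3, no shift: Mann-Whitney size rises to 8.4%.

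**The case against.** The reading of the plan is hard to dispute. The sentence concerns one group before and after training, and it follows a separate sentence on comparisons between groups. The case on the other side is about how much it matters.

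- **Scope.** The flaw touches one comparison under the secondary objective. The primary objective is assessed in theatre at 3 months only, and Mann-Whitney between the randomised groups is valid. A within-group change also cannot separate simulation training from ordinary experience in post. All of this stands.
- **Direction.** With positive correlation the error is conservative: it hides improvement and does not invent it. Inflation needs a negative correlation, which is implausible for repeated skill scores. This stands too.
- **Size.** The loss depends on figures that the documents do not give. It is nil at zero correlation, and 7 points (91% against 98%) for a 0.8 SD shift at ρ = 0.5. It is large only when correlation is moderate or high and the shift is modest.
- **Scale.** Part of the gain from a signed-rank test on logs comes from the transform. On raw differences the gain is smaller but remains substantial at ρ of 0.5 or more.
- **Other evidence.** The sensors will also be judged by between-group results, global rating scales, questionnaires and performance by experience. No passage makes this p-value decisive.

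These points limit the consequence. They do not make the test valid: its nominal error rate is right only if a trainee's two scores are unrelated.

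**Conclusion.** The concern holds. Section 8.1 specifies an independent-samples test for paired data, and nothing elsewhere corrects it. At 30 pairs and a 0.5 SD improvement, discarding the pairing costs about 12 power points at ρ = 0.3, 27 at ρ = 0.5 and 46 at ρ = 0.7 (raw differences, log-scale SD 0.5). The true type I error falls to between 2.2% and 0.1%. These sizes rest on an assumed correlation, shift, 5% level and log-normal shape. That the p-values are wrong whenever the two scores correlate does not rest on them. Recruiting more trainees, which Section 8.2 allows, would raise the power of both tests but would not restore the error rate. The harm is missed learning effects in the within-group simulator analysis, and nowhere else.

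**What to change.** Replace the within-group sentence in Section 8.1 with wording such as: *Within-group change on the simulator from baseline to 3 months will be tested with the Wilcoxon signed-rank test on paired values at the two-sided 5% level, and reported as the Hodges-Lehmann estimate of the change with a 95% confidence interval.* Keep Mann-Whitney and Kruskal-Wallis for independent groups only.

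A log transform is optional. If it is used, say so in advance and report the back-transformed estimate as a ratio of 3-month to baseline values, because it is no longer a difference in movements or path length.

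The cost is one sentence. No new data or procedures are needed, since the identifiers already allow the two assessments to be linked. Trainees with only one assessment drop out of this test, and their number should be reported.
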